6.1.6 Storage Conditions

XRB Storage Conditions: Store refrigerated at 2 - 8°C (35.6 - 46.4°F). Once outside the refrigerator XRB may be stored in its original package at room temperature 15-30°C (59-86°F), for up to 7 days prior to administration.

SLB Storage Conditions: Store at room temperature between 20 - 25°C (68 - 77°F).

6.1.7 Concomitant therapy

It is advisable for both XRB and SLB treatment arms that patients refrain from use of benzodiazepines, sedatives, tranquilizers, antidepressants, stimulants, or alcohol. Urine toxicology will be collected at medication dispensation visits in order to ensure no contraindications.

6.1.8 Restrictions

XRB Restrictions: For abdominal subcutaneous injection only. Do not administer XRB intravenously or intramuscularly. Only a healthcare provider should prepare and administer XRB. Administer monthly with a minimum of 26 days between doses.

SLB Restrictions: Take the prescribed dose once a day. SLB must be taken whole. Do not cut, chew, or swallow. SLB film should not be moved after placement. Proper administering technique should be demonstrated to the patient by a healthcare provider.

6.2 Assessments

Measures and Assessments:

- a) Baseline assessments include a drug and alcohol use history (ASI-Lite), a pre-arrest recall of drug and alcohol use (Timeline Followback), a medication treatment for opioid use disorder exposure/preference form (MOUD preference), demographic information, and jail Electronic Medical Record medical and psychiatric history and laboratory data, including HIV and HCV status.
- b) In-jail feasibility assessments of XRB vs. SLB include logging the % eligible enrolling in the study; the density of medical/nursing/pharmacy visits per arm and per participant; the incidence rates of medication diversion; open-ended interviews with participants surrounding XRB vs. SLB and ease-of-use and satisfaction;
- a) Post-release follow-up assessments include administrative data for SLB medication refills and post-release XRB injections, self-reported opioid and other drug use (Timeline Followback), urine toxicology testing, pregnancy testing, treatment retention (treatment retention form), Adverse Event and Serious Adverse Event monitoring (SAFTEE), and NYS Prescription Monitoring Data for community SLB pharmacy refill reporting. The I-STOP/PMP (prescription monitoring program) registries will be accessed in order to track participant data related to respective treatments. Additional qualitative interviews will be conducted with eligible XRB participants to further examine opioid use disorder treatment with extended-release buprenorphine, in-jail and within the community.

6.2.1 Efficacy

The primary outcome of in-jail feasibility and acceptability will be measured by the percent of eligible participants who enroll in the study, the mean medical/medication visits per arm and per participant, the incidence rates of medication diversion, and open-ended interviews with patients regarding treatment satisfaction and ease of use.

Secondary Aims 1-3 will be measured utilizing the following assessments: baseline demographics, baseline ASI-Lite, baseline MOUD exposure/preference, Timeline Followback, urine toxicology results, treatment retention, and NYS Prescription Monitoring Data. XRNTX, ETAU, and Methadone outcomes will be taken from the SOMATICS-XOR U01 parent study.

6.2.2 Safety/Pregnancy-related policy

XRB and SLB are both FDA approved, safe, efficacious medications for the treatment of opioid use disorder. As with most medications both XRB and SLB carry side effects as detailed above. Participants will be monitored throughout this pilot RCT by study physicians, all adverse events and/or serious adverse events will be documented and medication will be discontinued if necessary. Women who are pregnant or plan to become pregnant will be excluded from this pilot RCT.

6.2.2.1 Adverse Events Definition and Reporting

For the purposes of this pilot, proof-of-concept, RCT, an adverse event (AE) is any symptom, sign, illness or experience that develops or worsens in severity during the course of the study. Intercurrent illnesses or injuries should be regarded as adverse events.

Abnormal results of diagnostic procedures are considered to be adverse events if the abnormality:

- results in study withdrawal
- is associated with a serious adverse event
- is associated with clinical signs or symptoms
- leads to additional treatment or to further diagnostic tests
- is considered by the investigator to be of clinical significance (i.e. medication side effects)

All adverse events will be documented in the attached clinical research form and reported to the IRB where necessary.

A **serious adverse event** (SAE) is any AE that is:

- fatal
- life-threatening
- requires or prolongs hospital stay
- results in persistent or significant disability or incapacity
- a congenital anomaly or birth defect
- an important medical event

Important medical events are those that may not be immediately life threatening, but are clearly of major clinical significance. They may jeopardize the subject, and may require intervention to prevent one of the other serious outcomes noted above. For example, drug overdose or abuse, a seizure that did not result in in-patient hospitalization, or intensive treatment of bronchospasm in an emergency department would typically be considered serious.

All serious adverse events will be documented in the attached clinical research form and reported to the IRB where necessary.

Classification of an Adverse Event: for AEs in this pilot RCT the following guidelines will be used to describe severity.

- Mild — Events require minimal or no treatment and do not interfere with the participant's daily activities.
- Moderate — Events result in a low level of inconvenience or concern with the therapeutic measures. Moderate events may cause some interference with functioning.
- Severe — Events interrupt a participant's usual daily activity and may require systemic drug therapy or other treatment. Severe events are usually potentially life-threatening or incapacitating.

Relationship to Study Medication: To assess whether an AE may be associated with the study medication (XRB vs. SLB) the following guidelines will be used:

- **Definitely Related** — There is clear evidence to suggest a causal relationship, and other possible contributing factors can be ruled out. The clinical event, including an abnormal laboratory test result, occurs in a plausible time relationship to drug administration and cannot be explained by concurrent disease or other drugs or chemicals. The response to withdrawal of the drug (dechallenge) should be clinically plausible. The event must be pharmacologically or phenomenologically definitive, with use of a satisfactory rechallenge procedure if necessary
- **Probably Related** — There is evidence to suggest a causal relationship, and the influence of other factors is unlikely. The clinical event, including an abnormal laboratory test result, occurs within a reasonable time after administration of the drug, is unlikely to be attributed to concurrent disease or other drugs or chemicals, and follows a clinically reasonable response on withdrawal (dechallenge). Rechallenge information is not required to fulfill this definition.
- **Possibly Related** — There is some evidence to suggest a causal relationship (e.g., the event occurred within a reasonable time after administration of the trial medication). However, other factors may have contributed to the event (e.g., the participant's clinical condition, other concomitant events). Although an AE may rate only as "possibly related" soon after discovery, it can be flagged as requiring more information and later be upgraded to "probably related" or "definitely related," as appropriate.
- **Unlikely to be related** — A clinical event, including an abnormal laboratory test result, whose temporal relationship to drug administration makes a causal relationship improbable (e.g., the event did not occur within a reasonable time after administration of the trial medication) and in which other drugs or chemicals or underlying disease provides plausible explanations (e.g., the participant's clinical condition, other concomitant treatments).
- **Not Related** — The AE is completely independent of study drug administration, and/or evidence exists that the event is definitely related to another etiology. There must be an alternative, definitive etiology documented by the clinician.

Study clinicians will be responsible for determining whether an AE is expected or unexpected. An AE will be considered unexpected if the nature, severity, or frequency of the event is not consistent with the risk information previously described for the study agent.

The pilot study team will record all reportable events with start dates occurring any time after informed consent is obtained until 7 (for non-serious AEs) or 30 days (for SAEs) after the last day of study participation. At each study visit, the investigator will inquire about the occurrence of AE/SAEs since the last visit. Events will be followed for outcome information until resolution or stabilization.

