(7) Where the Board finds there may be a need for follow-up examination or care of participants after the end of their participation, adequate provision has been made for such examination or care, taking into account the varying lengths of individual prisoners' sentences, and for informing participants of this fact. The study primarily consists of community follow-up of adults released from NYC jails. Follow-up consists of research visits conducted weekly then bi-weekly for both medication arms post-release (week 1 post-release, week 2, week 4, week 6, week 8). After the completion of Visit 5 Week 8, all participants will be eligible for a 24 week therapeutic extension study wherein they are offered initial and/or additional XRB injections. These will occur monthly post study week 8: week 12, week 16, week 20, week 24, and week 28. A final safety visit, no medication administered, will be conducted at week 32 to document safety reporting and provide post-study treatment referrals.

6 - Methods

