6.3.1 Study Schedule

The total number of expected visits per participant is 6 visits. All participants will be given the option to participate in a 24 week therapeutic extension study of XRB treatment following completion of Visit 5 Week 8. If a participant elects to continue and/or initiate XRB treatment, there will be 12 total visits per participant. The average time needed to complete each visit will be approximately one hour. The initial week 0 screening and randomization visit will be conducted in a Rikers Island jail facility in the Opioid Treatment Program. Once consented, enrolled, and randomized, buprenorphine extended-release (XRB) or sublingual buprenorphine (SLB) daily maintenance will be provided per usual Opioid Treatment Program protocols in-jail and prior to release. The timing between randomization and release will vary. Typical misdemeanor sentences in NYC are 30-60 days, and participants may randomize at any time during this incarceration period, begin XRB vs. SLB treatment, and then leave jail after weeks-to-months. This variable, naturalistic, in-custody study period remains Study Week 0. Study Week 1 commences with the day of release from jail. Post-release, all study visits will be conducted at Bellevue Hospital Center's (BHC) Addiction Medicine clinic. Medical and research visits will be conducted weekly and then bi-weekly for both medication arms post-release (week 1 post-release, week 2, week 4, week 6, week 8). The medication schedule for both arms is as follows:

Buprenorphine Extended-Release: Participants randomized to this arm will receive at least two doses of XRB. The first will be administered at study week 0 in-jail, at least one week prior to release. Participants incarcerated for greater than 4 weeks following randomization will receive 2+ XRB doses prior to release. Post-release, XRB injections will be administered at study week 1-16 in the BHC Addiction Medicine clinic depending on the timing of the previous pre-release/community injections.

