6.3.5 On Study Visits

Screening and Randomization (~1.5 hours):

- Informed Consent & Informed Consent Quiz
- Baseline assessments:
 - Drug and alcohol use history (ASI-Lite)
 - Pre-arrest recall of drug and alcohol use (Timeline Followback)
 - Prior Medication Treatment for Opioid Use Disorder exposure & preferences (MOUD Preference form)
 - Jail Electronic Medical Record medical and psychiatric history & laboratory data, including HIV and HCV status
- Randomization envelope opened & completed by study staff and participant
 - Medication dispensed (XRB or SLB)
 - *Additional in-jail injections of XRB may occur if participant is incarcerated for over 4 weeks.*

Follow-Up Visits (v1-4, ~1 hour)

- Administrative data for SLB medication refills and post-release XRB injections
- Self-reported opioid and other drug use (Timeline Followback)
- Urine specimen collection and toxicology testing
- Adverse Event and Serious Adverse Event monitoring (SAFTEE)
- NYS Prescription Monitoring Data for community SLB pharmacy refill reporting
 - I-STOP/PMP Registry
- Treatment Retention Form completed
- *At visit 1 week 1, open-ended interview will be administered.*

- *At visit 3 week 4, second XRB administered, depending on prior injection date.*
- *At visit 3 week 4, pregnancy test will be administered..*

Research Visit 5 Week 8 (Final Visit, ~1 hour):

- Medication is not dispensed
- For participants electing to continue in the 24 week extension, initial and/or additional XRB injection could be administered at this time point
- Self-reported opioid and other drug use (Timeline Followback)
- Urine specimen collection and toxicology testing
- Pregnancy testing
- Treatment Retention completed
- Treatment Satisfaction completed
- Adverse Event and Serious Adverse Event monitoring (SAFTEE)
- NYS Prescription Monitoring Data for community SLB pharmacy refill reporting
 - I-STOP/PMP Registry
- Open-ended interview with participants concerning XRB vs. SLB treatment satisfaction and ease-of-use

Treatment Visit 6-10 Week 12, 16, 20, 24, 28 (~1 hour):

- 24 Week Extension Participants Only:
 - Self-reported opioid and other drug use (Timeline Followback)
 - Urine specimen collection and toxicology testing
 - Adverse Event and Serious Adverse Event monitoring (SAFTEE)
 - *XRB administered, depending on prior injection date.*
 - *At visit 7 week 16 and visit 10 week 28, pregnancy test will be administered*

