6.3.7 Removal of subjects

Participation in this pilot, proof-of-concept, RCT is entirely voluntary and participants are free to withdraw at any time. In the event of early study termination, study staff will complete the study termination form, modeled from a CRF of the parent XOR study. Any participant withdrawing from the study prior to full study completion, regardless of study group, stands a risk of relapsing to illicit opioid or other drug/alcohol misuse. The study will assist with treatment referrals for detox services at Bellevue Hospital Center, but will not otherwise directly provide such services or medications. Otherwise any XRB or SLB patient who has relapsed and is not interested in continuing their baseline study condition (i.e., an XRB participant does not wish to continue injections due to side effects or for any other reason) will be encouraged to pursue other appropriate community treatment, the menu of which includes the robust addiction service offerings at Bellevue Hospital Center (BHC). BHC's services are available to all persons, regardless of insurance status or an ability to pay, and include emergency detox inpatient services, methadone treatment, office-based buprenorphine, and intensive outpatient and dual diagnosis programs. These services will consist of usual care occurring outside of the study and will not be directly provided by or paid for by the study.

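### The 7-day window for non-serious adverse events is not tied to the last XRB injection, so it can close before one dosing interval has passed for early leavers and off-schedule injections

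*Combined protocol and SAP*

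**What the plan says.** Section 6.2.2.1 records events from consent "until 7 (for non-serious AEs) or 30 days (for SAEs) after the last day of study participation". During the study, "At each study visit, the investigator will inquire about the occurrence of AE/SAEs since the last visit". Events already recorded are followed until they resolve or stabilise, but that rule does not reach events that start after the window closes.

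Section 6.1.8 says of XRB: "Administer monthly with a minimum of 26 days between doses". Section 6.3.5 places the usual post-release injection as follows: "At visit 3 week 4, second XRB administered, depending on prior injection date". Section 6.3.1 allows wider timing: "Post-release, XRB injections will be administered at study week 1-16 in the BHC Addiction Medicine clinic depending on the timing". The dispensing row of the schedule table also shows XRB at Week 6, although the XRB administration form row does not.

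Section 6.3.6 ends participation at Week 8, or at Week 32 for those in the extension. It gives no end date for anyone who withdraws or is lost. For the extension, section 5.3.2 states: "A final safety visit, no medication administered, will be conducted at week 32 to document safety reporting". Section 6.3.7 allows withdrawal at any time and adds no event follow-up counted from the last injection.

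**The concern.** A post-treatment safety window normally outlasts the effect of the last dose given. Here the non-serious window is 7 days for a product dosed monthly, and it is counted from the end of participation. Whether it spans a full dosing interval therefore depends on when the person happens to leave. The 30-day serious-event window does span one, and so does the no-medication safety visit placed 4 weeks after the last planned extension injection. Only the non-serious window can fall short.

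The XRB risks named in section 3.3.2 are systemic buprenorphine effects and injection-site soreness, swelling, itching and pain. Most events of this kind would be non-serious. Acceptability and in-treatment satisfaction are primary outcomes, and incomplete tolerability data in people who leave soon after an injection would make those outcomes harder to interpret.

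**Working it through.** The plan gives no figure to reproduce; the check is a day count.

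**Inputs**
- Non-serious window: 7 days after the end of participation (6.2.2.1).
- Serious-event window: 30 days after the same point (6.2.2.1).
- Dosing interval D: 26 days is the stated minimum (6.1.8). D = 28 (four-week schedule) and D = 30 (calendar month) are assumed readings of monthly.
- t: days from the last injection to the final day of participation.

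**Formula.** Days of the interval without non-serious event collection = max(0, D − 7 − t).

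| Case | t | D = 26 | D = 28 | D = 30 |
|---|---|---|---|---|
| Final day is an injection day | 0 | 19 (73%) | 21 (75%) | 23 (77%) |
| Injected Week 6, exit Week 8 | 14 | 5 (19%) | 7 (25%) | 9 (30%) |
| Injected Week 4, exit Week 8 | 28 | 0 | 0 | 0 |
| Last planned extension injection, then safety visit | 28 | 0 | 0 | 0 |

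In the last two rows observation runs 28 + 7 = 35 days. The extension row holds under either version of the schedule. Section 5.1.1 puts the last treatment at Week 20 and the safety visit at Week 24; section 5.3.2 and the schedule table put them at Weeks 28 and 32. The two versions need reconciling, but both leave 28 days.

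**When is more than half the interval uncovered?** D − 7 − t > D/2 gives t < D/2 − 7, that is t < 6, 7 or 8. The person must leave within 5, 6 or 7 days of the injection for D = 26, 28 or 30. The gap is zero from t = D − 7, that is from day 19, 21 or 23.

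**Can a Week 6 injection occur?** A jail dose given 14 days before release, followed at 28-day intervals, falls at −14 + 28 = day 14 (Week 2) and 14 + 28 = day 42 (Week 6). Section 6.3.1 allows this timing.

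**Serious events.** The margin is 30 − 26 = 4, 30 − 28 = 2 or 30 − 30 = 0 days, so the interval is covered in every case.

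**Undefined start of the clock.** If the final day for a lost participant is the last attended visit, someone injected at Week 8 for the extension who never returns falls in the first row: 19 to 23 days. If it is the scheduled end of the study, the window stays open on paper, but the protocol does not say how events would be learned of.

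**The case against.** The strongest case on the other side has five parts, and most of it stands.

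- **The planned path has no gap.** Week 4 to Week 8 gives 35 days, and visits throughout ask about events. This is correct and confines the point to early leavers and off-schedule injections. A reader might infer that anyone leaving after an injection is unobserved for most of the interval. That holds only for exit within about 5 to 7 days, and only for non-serious events.
- **The arms may not differ as they seem to.** A reader might infer that a 7-day cut-off truncates XRB but not daily SLB, so that XRB tolerability looks better than it is. The protocol does not support this. SLB participants receive 2- to 4-week refills (6.3.1), and most participants in both arms are expected to continue SLB afterwards (6.3.6). Exposure can therefore outlast the window in both arms.
- **Stopping injections is not leaving the study.** Section 6.3.7 mentions the case where "an XRB participant does not wish to continue injections due to side effects or for any other reason". That concerns the assigned treatment, and nothing says that participation then ends. It does not show that people with side effects are the ones lost to collection.
- **26 days is a dosing interval.** The protocol gives no duration of drug exposure, so the day counts measure coverage of the interval, not of exposure.
- **The consequence is limited.** Section 6.4.1 plans no between-arm analysis of adverse events, and serious events, for which section 6.2.2.1 gives overdose as an example, have the longer window.

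None of this removes the shortfall for a participant who leaves at or soon after an injection.

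**Conclusion.** The point holds within limits. The non-serious window is tied to the end of participation and not to the last injection, and its start is undefined for early terminations. The shortfall is at least 19 of 26 days when the final day is an injection day (19 to 23 days over the assumed readings of monthly), 5 to 9 days for a Week 6 injection with a Week 8 exit, and zero on the usual planned paths.

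This assumes that one dosing interval is a reasonable minimum span for asking about events after an injection and, for lost participants, that the last attended visit counts as the final day. The documents give no dropout figures by time since injection, so the number affected cannot be computed. Neither the existence nor the direction of any between-arm bias can be established. It is a worthwhile low-cost correction to safety collection and does not threaten the trial's main comparison.

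**What to change.** In section 6.2.2.1:

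1. Replace the 7-day window for non-serious events with the 30-day window already set for serious events, in both arms, ending no earlier than one dosing interval after any last XRB injection.
2. Define the final day of participation for those who withdraw or are lost, and repeat the definition in section 6.3.7.
3. Ask about non-serious events in the same inquiry that ascertains serious events to 30 days, for early terminations as well as completers.

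The cost is a few sentences and some additional recording. Changing the window alone will not collect more data: the schedule shows no visit or call after the final visit, so the protocol must also say how the 30-day inquiry it already requires is made. Making that inquiry explicit may take some staff effort, but the serious-event rule already needs it.

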Sublingual Buprenorphine (SUBOXONE, Zubsolv, or generic tablets): SLB is administered sublingually or buccally as a single daily dose. Medication should be prescribed in consideration of the frequency of visits. Provision of multiple refills is not advised in early treatment or without appropriate follow-up visits. After treatment induction and stabilization, the maintenance dose of SLB is generally in the range of 4mg/1mg buprenorphine/naloxone to 24mg/6mg buprenorphine/naloxone per day depending on the individual patient and clinical response, as determined by the clinician. Daily doses will vary by individual. The recommended target dose of SLB during maintenance is 16mg/4mg buprenorphine/naloxone. SLB will be prescribed and provided via observed dosing in-jail (controlled substances are not self-administered in-jail) per usual care protocols. Post-release, all participants may elect to continue SLB maintenance with the Bellevue Primary Care Addiction Medicine clinic, or may pursue SLB maintenance from non-NYU/Bellevue community providers. SLB is available free of charge to uninsured patients at Bellevue Hospital Center, or participants may fill SLB prescriptions at community pharmacies. SLB medication will not be provided by the study itself. Self-report, BHC EMR records, and NYS Prescription Monitoring Plan audits will document SLB post-release community treatment retention, daily dose, and refill frequencies.

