Sublingual Buprenorphine: Participants randomized to this arm will be provided SLB daily maintenance per usual Opioid Treatment Programs protocols in-jail. Post-release, SLB arm participants will receive follow-up care at Bellevue Hospital's Addiction Medicine or at non-BHC/NYU community providers, per their preference. We expect and will encourage most participants to follow-up at Bellevue, though this is not mandated. Typically an initial week's supply of SLB is prescribed within one week of release. At visit 2, week 2, SLB participants typically refill a two week's supply of daily maintenance SLB. SLB participants will continue to receive 2-4 week refill prescriptions for SLB from visit 2, week 2 through visit 6, week 8. Regardless of SLB prescribing patterns, they are encouraged to attend study follow-up visits at BHC per the same study schedule (Weeks 1,2,4,6,8). After the completion of Visit 5 Week 8, SLB participants will be offered XRB treatment in the 24 week therapeutic extension. If interested, participants would receive one or more XRB injections during the

period of Weeks 8, 12, 16, 20, 24, and 28 followed by a final safety documentation visit at Week 32.

For both treatment arms, urine toxicology tests will be conducted at all follow-up visits at the BHC Addiction Medicine Clinic in order to detect any illicit substance use as well as buprenorphine adherence.

STUDY SCHEDULE												
Test/Procedures	Screening/ Randomization	Treatment Period & Follow-Up					XR-B 20 Week Treatment & Follow-Up					
Study Visit Number	0	1	2	3	4	5	6	7	8	9	10	11
Week	0	1	2	4	6	8	12	16	20	24	28	32
Informed Consent ¹	X											
HIPAA ²	X											
Locator Form	X											
Medical History	X											
Psychological History	X											
Physician Progress Note	X	X	X	X	X	X	X	X	X	X	X	X
Confirm Eligibility	X											
Randomization	X											
Adverse Event Forms (AE, SAE, BUP specific AE)		X	X	X	X	X	X	X	X	X	X	X
Clinical Assessment of Intervention ³						X						X
Urine Toxicology		X	X	X	X	X	X	X	X	X	X	X
Pregnancy Test				X		X		X			X	
Demographics	X											
MOUD History/Preference	X											
ASI-Modified Lifetime/CJS-Baseline	X											
Timeline Followback	X	X	X	X	X	X	X	X	X	X	X	X
Inmate Lookup Form⁴		X	X	X	X	X						
New Arrests and Days Incarcerated Form⁴		X	X	X	X	X						
Overdose Form		X	X	X	X	X	X	X	X	X	X	X
XR-B Administration Form	X			X			X	X	X	X	X	

NYS Prescription Monitoring Data (SLB- Only)		X	X	X	X	X						

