6.4.3 Handling of Missing Data

Follow-up among individual participants at Bellevue Hospital is encouraged with XOR's monetary incentives and tracking protocols. Participants in either arm choosing buprenorphine f/u at Bellevue will be particularly likely to complete follow-up. Administrative and program data covering community pharmacy fills of buprenorphine products and community provider reporting will be used to supplement treatment retention outcomes (Aim 2). Missing opioid urine toxicology data is considered MissingAsPositive.

7 - Trial Administration

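### Serious events after release are sought only at Bellevue visits, so those in participants who stop attending will tend to be under-counted

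*Combined protocol and SAP*

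**What the plan says.** Section 6.2.2.1 describes how events are found: "At each study visit, the investigator will inquire about the occurrence of AE/SAEs since the last visit". Recording starts at consent and runs "until 7 (for non-serious AEs) or 30 days (for SAEs) after the last day of study participation". The same section uses overdose to illustrate an event that would typically be serious: "For example, drug overdose or abuse, a seizure that did not result in in-patient hospitalization".

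Section 6.3.1 fixes where and when the question is put. "Post-release, all study visits will be conducted at Bellevue Hospital Center's (BHC) Addiction Medicine clinic", and in the randomised period these fall at "week 1 post-release, week 2, week 4, week 6, week 8". In the schedule table, the adverse event forms and the "Overdose Form" are marked against visits 1 to 11.

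Other sources are named, but for another purpose. In section 6.1.5, "Self-report, BHC EMR records, and NYS Prescription Monitoring Plan audits will document SLB post-release community treatment retention". Section 6.4.3 uses pharmacy and provider data to supplement retention, and counts missing opioid urine results as positive. It has no rule for missing safety reports. It also expects attendance to go with treatment site: "Participants in either arm choosing buprenorphine f/u at Bellevue will be particularly likely to complete follow-up".

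**The concern.** The protocol recognises that some people will miss visits and provides for this in its retention and urine outcomes, but not in its safety data. No section describes a search of hospital or death records for overdoses, admissions or deaths, or says how such an event would come to light in someone who never returns. A participant who has died cannot be asked at the next visit.

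This matters because section 3.3.2 names death and disability from relapse after release as a risk, and section 3.1 points to worsening overdose rates that include people recently in jail. Under section 7.8 the DSMB reviews adverse and serious events, and clear evidence of harm is among its stopping conditions. Section 7.10 allows termination for unacceptable adverse events.

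There is also a route by which capture could differ by arm. Post-release XRB is injected at Bellevue, whereas SLB participants may be treated by outside providers (section 6.3.1). If that makes attendance unequal, the recorded event counts are not comparable between arms.

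**Working it through.** **The plan's own figure.** The documents give no attendance, dropout or safety event rate. The only relevant inputs are the Week 4 retention rates in section 6.4.2: 71% (XRB) and 30% (SLB), N=50, two-sided alpha 0.05, power of 80% or more. With 25 per arm and a pooled rate of 0.505:

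- null standard error = √(2 × 0.505 × 0.495 / 25) = 0.1414
- alternative standard error = √((0.71 × 0.29 + 0.30 × 0.70) / 25) = 0.1290
- z = (0.41 − 1.96 × 0.1414) / 0.1290 = 1.03, giving power of 84.8%. Fisher's exact test gives 80.5%.

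The stated power reproduces, so the retention rates are used below as the plan gives them.

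**Assumptions (not in the documents).** Attendance of 90% among retained participants and 90%, 70%, 50% or 30% among the non-retained. Event risk of 5% among the retained, and either 5% (equal) or 15% (threefold) among the non-retained. Attending means being asked at some visit after the event.

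**Formulas.** Let r be the retained share, a_R and a_N attendance, and p_R and p_N risk, in retained and non-retained participants.

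- share reachable = r·a_R + (1 − r)·a_N
- true risk = r·p_R + (1 − r)·p_N
- recorded risk = r·p_R·a_R + (1 − r)·p_N·a_N

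**Worked case, a_N = 50%.**

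- Reachable: XRB 0.71 × 0.9 + 0.29 × 0.5 = 0.784; SLB 0.30 × 0.9 + 0.70 × 0.5 = 0.620. With equal risk the recorded SLB/XRB ratio is 0.620 / 0.784 = 0.79.
- Threefold risk, true: XRB 0.71 × 0.05 + 0.29 × 0.15 = 0.079; SLB 0.30 × 0.05 + 0.70 × 0.15 = 0.120; ratio 1.52.
- Threefold risk, recorded: XRB 0.0355 × 0.9 + 0.0435 × 0.5 = 0.0537; SLB 0.015 × 0.9 + 0.105 × 0.5 = 0.0660; ratio 1.23.

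| Attendance of non-retained | Reachable, XRB | Reachable, SLB | Recorded SLB/XRB ratio, equal risk (true 1.00) | Recorded SLB/XRB ratio, threefold risk (true 1.52) |
|---|---|---|---|---|
| 90% | 90% | 90% | 1.00 | 1.52 |
| 70% | 84% | 76% | 0.90 | 1.39 |
| 50% | 78% | 62% | 0.79 | 1.23 |
| 30% | 73% | 48% | 0.66 | 1.00 |

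**When the order reverses.** Setting recorded SLB risk below recorded XRB risk and cancelling the common factor of 0.41 leaves p_N·a_N < p_R·a_R. With threefold risk and a_R = 90%, this needs a_N below 30%.

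**Counts.** With threefold risk, 25 per arm gives 25 × 0.079 = 1.98 true events on XRB and 25 × 0.120 = 3.00 on SLB. At a_N = 50%, 1.34 and 1.65 are recorded. With so few events, one or two missed cases change the table.

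**The case against.** The strongest reply is that the protocol does more than wait for people to attend:

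- Section 5.1.2 has staff track lost participants in the community, including visits to their homes.
- Section 6.3.1 encourages SLB participants to keep the same visit schedule wherever they are treated, and expects most to choose Bellevue. Section 3.3.1 gives both arms the same compensation.
- The inquiry looks back to the last visit, so an event in someone who misses a visit and later returns is recovered.
- Section 6.3.6 says safety monitoring continues over the whole study.

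All of this stands and limits the loss to people who do not return, and to deaths. It does not close the gap: neither the tracking nor the monitoring text says that safety questions are asked, or records searched, when a participant stays away.

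A reader might go further and infer that the arm with more dropout will look safer, perhaps by a factor of 0.71 / 0.30 = 2.4. The documents do not support that. The factor treats retention with any provider as attendance at Bellevue and assumes that no event among the non-retained is ever found. Apparent safety in the arm with more dropout requires the loss of capture to outweigh any higher risk in dropouts. With threefold risk, the illustration weakens the SLB/XRB ratio from 1.52 to between 1.39 and 1.00 but does not reverse it.

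The direction by arm is also unsettled. Section 6.4.3 ties attendance to Bellevue care in both arms. Before the extension the XRB administration form is marked only at Weeks 0 and 4, though timing varies with release date. SLB participants typically need a prescription within a week of release and a refill at Week 2, so those treated at Bellevue may have more reason to attend early.

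Finally, this is an exploratory pilot with no named safety outcome or planned comparative safety analysis, which limits how much weight the point carries.

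**Conclusion.** The gap is real. As described, post-release adverse events, serious events and overdoses are elicited only at Bellevue visits, so those in participants who stop attending, deaths included, will tend to be under-counted. Distortion between arms is conditional: it needs attendance to differ by arm, which is plausible but neither stated nor quantified.

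Under the assumed attendance and risks, with the plan's 71% and 30% retention, equal true risk is recorded as a ratio of 0.90 to 0.66, and a true ratio of 1.52 as 1.39 to 1.00. If retained and non-retained participants attend equally, the ratio is undistorted. The point leaves the feasibility aim and the retention analysis untouched. It bears on the safety data the DSMB will see, where about one to three true events per arm would be expected under these risks.

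**What to change.** In section 6.2.2.1:

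- (a) Ask about overdose, emergency or hospital care, and death at every tracking contact as well as at clinic visits. The answer may come from the participant or from locator contacts.
- (b) At Week 8 plus 30 days, check the Bellevue record for the same events in all randomised participants in both arms. The study already uses this record for SLB retention. Use the Inmate Lookup only to establish custody status, since nothing in the protocol says it identifies overdose, admission or death.
- (c) Report these events by randomised arm over all randomised participants, separately from visit-reported events, with the completeness of safety follow-up in each arm. Show events up to Week 8 apart from later ones, because XRB is offered to both arms from Week 8.

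The cost is about 50 record checks, a few staff hours, and confirmation that record access and the consent and HIPAA scope cover this use in both arms. Events treated outside that hospital system will still be missed, and the report should state this as a limitation. No visit, treatment or sample size changes.
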